13.13 Expedited Reporting of Suspected Unexpected Serious Adverse Reactions (SUSARs)

Study sponsor, Fundación Zero LMC, is responsible for reporting suspected, unexpected, serious adverse reactions involving the study drug to all regulatory authorities and participating investigators in accordance with ICH Guidelines and/or local regulatory requirements, as applicable.

The sponsor will notify investigators of all reportable SAEs. This notification will be in the form of an expedited safety report (ESR). Upon receiving such notices, the investigator must review and retain the notice with other study-related documentation.

Suspected serious adverse reactions and other significant safety issues reported from the investigational product development program will be reported by the sponsor or its designated representative—either as expedited safety reports and/or in aggregate reports—to the relevant, competent health authorities in all concerned countries.

13.14 Contraception and Pregnancy

Females of childbearing potential and fertile males will be informed of the potential risk of conception while participating in this study. Females of childbearing potential are required to use a highly effective form of contraception from recruitment through at least 4 months after the end of treatment (see inclusion criterion 7)

A pregnancy test will be performed on each premenopausal female of childbearing potential within 7 days prior to first dose of bosutinib, and again each month during the study, at the end-of-treatment visit and at the end-of-study visit. A negative pregnancy test must be documented prior to administration of study drug.

Females should be advised to take a pregnancy test if their period is late, and to inform their investigator of the result.

If a patient is confirmed pregnant during the trial, study drug administration must be discontinued immediately. The investigator must also immediately notify the sponsor medical monitor of this event and record the pregnancy on a pregnancy form. Initial information regarding a pregnancy must be immediately (in less than 24 hours) forwarded to FTH Pharmacovigilance and Risk Management or its designated representative.

The investigator must immediately report follow-up information to the sponsor regarding the course of the pregnancy, including perinatal and neonatal outcomes, regardless of whether the patient has discontinued participation in the study. If the pregnancy results in the birth of a child, additional follow-up information may be requested. If the pregnancy results in spontaneous abortion or stillbirth, that event should be reported as a SAE.

Pregnancy outcomes must also be collected for the female partners of any males who took study drug in this trial. Consent to report information regarding these pregnancy outcomes should be obtained from the female partner.

13.15 Overdose, medication error, abuse, misuse

An overdose is defined as the accidental or intentional ingestion or infusing of any dose of study treatment that exceeds the dose described in the protocol. Overdoses are not considered AEs; however, all overdoses should be recorded and forwarded to FTH Pharmacovigilance and Risk Management or its designated representative within 24 hours. An overdose should be reported even if it does not result in an AE. Overdoses do not need to be recorded on the eCRF; dosing information is recorded on the form.

Other special situations such as medication error (including intercepted or potential medication error), abuse and misuse are not considered AEs. However, they should be also recorded and forwarded to FTH within 24 hours.

14 CO-TREATMENT AND TREATMENT SUPPLY

14.1 Prior and Concomitant Treatment

All concomitant medications administered from the time of informed consent signature until 28 days after end of treatment (either the last dose of study drug or the investigator/patient decision to discontinue, whichever occurs later), are to be recorded in the patient's eCRF.

14.2 Permitted Treatment

All routine and appropriate supportive care (including receipt of blood products and hematopoietic growth factors) will be allowed during this study, as clinically indicated, and in accordance with standard-of-care practices. Clinical judgment should be utilized in the treatment of any AE experienced by an individual patient.

Information on all concomitant medications, administered blood products, and interventions occurring during the study must be recorded on each patient's eCRF. Among other treatments for concurrent illnesses, the following therapies are allowed:

- Rhu-EPO and G-CSF are allowed in case of anemia (Hb<12 g/dl) and/or neutropenia (ANC < 1000/mm³)
- Diuretics are allowed in case of fluid retention
- It may be necessary in some situations to administer corticosteroids, immunosuppressives, thyroid replacement hormone, anti-thyroid drug, insulin, antihistamine, anti-pyretic, epinephrine, bronchodilators, and oxygen in case of adverse events observed with atezolizumab.

14.3 Prohibited Treatments/Therapy

The following concurrent medications and treatments are prohibited:

- Other anticancer therapies
- Other investigational drugs or devices
- Medications that prolong the QT interval (see [Appendix A](#))
- CYP3A inhibitors (including, but not limited to itraconazole, ketoconazole, posaconazole, voriconazole, clarithromycin, telithromycin, nefazodone, mibefradil, indinavir, lopinavir/ritonavir, nelfinavir, ritonavir, saquinavir, boceprevir, telaprevir, grapefruit products including grapefruit juice) or moderate CYP3A inhibitors (including, but not limited to fluconazole, ciprofloxacin, erythromycin, diltiazem, verapamil, amprenavir, atazanavir, darunavir/ritonavir, fosamprenavir, aprepitant, crizotinib, imatinib), and strong CYP3A inducers (including, but not limited to carbamazepine, phenytoin,

rifampicin, St. John's Wort), or moderate CYP3A inducers (including, but not limited to bosentan, efavirenz, etravirine, modafinil, naftilin).

15 PLANNED STATISTICAL ANALYSIS

This is a phase Ib/II, single arm, open-label and dose-escalation study designed to determine the safety profile and the recommended phase III dose of bosutinib when administered in combination with atezolizumab in naïve patients with chronic myeloid leukemia in chronic phase.

15.1 Analysis Sets

15.1.1 Full Analysis Set

The full analysis set (FAS) comprises all patients who complete the first three phases of treatment (combination of bosutinib and atezolizumab) successfully.

15.1.2 Safety Set

The safety set (SS) includes all patients who received at least one dose of study medication. Reporting and analysis of safety information for these patients will be split into subsets by study phases.

15.1.3 Per-Protocol Set

The per-protocol set (PPS) consists of a subset of the patients in the FAS who are compliant with requirements of the clinical study protocol (CSP).

A compliance of 70% with bosutinib treatment will be necessary to be included in the PPS

Protocol deviations leading to exclusion from the PPS will be detailed in the Clinical Study Report.

15.2 Patient Demographics/other Baseline Characteristics

Demographic and other baseline data will be summarized descriptively for both the SS and the FAS. Categorical data will be presented as frequencies and percentages. For continuous data, mean, standard deviation, median, 25th and 75th percentiles, minimum, and maximum will be presented.

15.3 Primary Objective

The primary objective is to evaluate the safety profile of bosutinib 400 mg daily in combination with atezolizumab as first line treatments in participants with chronic myeloid leukemia.

15.3.1 Analysis Set and Grouping for the Analyses

The safety set population will be used for all safety analyses. Reporting of safety information for these patients will be split into subsets by first phase, second phase, third phase, and fourth phase.

15.3.2 Adverse Events

Summary tables for adverse events (AEs) have to include only AEs that started or worsened during the on-treatment period, the treatment-emergent AEs (TEAEs). However, all safety data (including those from the pre-treatment period) will be listed and those collected during the pre-treatment period are to be flagged.

The incidence of treatment-emergent adverse events (new or worsening from baseline) will be summarized by system organ class and/or preferred term, severity (based on CTCAE grades), type of adverse event, causality relation to study treatment by the phases or subsets previously described.

Deaths reportable as SAEs and non-fatal serious adverse events will be listed by patient and tabulated by type of adverse event and safety subset.

Specific safety event categories will be considered. Such categories consist of one or more well-defined safety events which are similar in nature and for which there is a specific clinical interest in connection with the study treatment(s).

For each specified safety event category, number and percentage of patients with at least one event part of the safety set will be reported. Also AESI will be summarized and analyzed.

15.3.3 Laboratory Abnormalities

For laboratory tests covered by the Common Terminology Criteria for Adverse Events (CTCAE) version 5.0 the study's biostatistician and reporting team will grade laboratory data accordingly. For laboratory tests covered by CTCAE, a Grade 0 will be assigned to all non-missing values not graded as 1 or higher. Grade 5 will not be used.

In some cases, (e.g., white blood cell differentials) the lower limits of normal ranges used in CTCAE definition have to be replaced by a clinically meaningful limit expressed in absolute counts.

For laboratory tests where grades are not defined by CTCAE, results will be graded by the low/normal/high classifications based on laboratory normal ranges.

The following by-safety subset summaries will be generated separately for hematology, and biochemistry tests:

- number and percentage of patients with clinically significant laboratory abnormalities, by parameter and worst post-baseline CTCAE grade. Each patient will be counted only for the worst grade observed post-baseline, regardless of the baseline status
- shift tables using CTCAE grades to compare baseline to the worst on-treatment value

- for laboratory tests where CTCAE grades are not defined, shift tables using the low/normal/high
- classification to compare baseline to the worst on-treatment value.
- listing of all laboratory data with values flagged to show the corresponding CTCAE grades and the classifications relative to the laboratory normal ranges.

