11.6.1.2 Hematologic Treatment-Related Toxicity

Dose reductions are recommended for severe or persistent neutropenia and thrombocytopenia. The management of hematologic treatment-related toxicities is summarized in Table 2.

Table 2. Hematologic Treatment-Related Toxicity

Adverse Event	Action
Grade 1	Current dose level
Grade 2	Current dose level
Grade 3 ^a	Withhold treatment: If recovered to Grade ≤ 2 within 2 weeks of treatment hold: re-introduce study drug at same dose. If recovered within 4 weeks of treatment hold: reduce study drug by 1 dose level. At subsequent occurrences of Grade 3 toxicity, dose must be reduced upon recovery to Grade ≤ 2 . If recovery takes longer than 4 weeks, the Investigator should contact the Sponsor to determine if the patient may continue on treatment.
Grade 4 ^a	Withhold treatment. Investigator and Sponsor to review to determine if patient may continue on treatment with appropriate dose reduction. 
a. For patients requiring dose reduction due to toxicity, who have been free of the toxicity (Grade ≤ 1) for at least 1 month and are otherwise tolerating study drug, the Investigator may choose to re-escalate dose by 1 dose level back to starting dose

Subjects fulfilling criteria for dose escalation due to suboptimal response, but also exhibiting Grade 2 hematologic treatment related toxicity will be eligible for dose escalation; however, if hematologic toxicity increases to Grade 3 or 4 after dose escalation, the subject will be managed as per the instructions for Grade 3 or 4 hematological toxicities in Table 2.

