13.2 Abnormal Test Findings

The criteria for determining whether an abnormal objective test finding should be reported as an AE are as follows:

- Test result is associated with accompanying symptoms that are considered clinically significant in the opinion of the investigator.
- Test result requires additional diagnostic testing (other than merely repeating an abnormal test) or medical/surgical intervention.
- Test result leads to a change in study drug dosing or discontinuation from the study, significant additional concomitant drug treatment, or other therapy.
- Test result is considered to be clinically significant by the investigator or sponsor.

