13.9.1 Adverse Event of Special Interest

AESIs require ongoing monitoring by investigators and rapid identification and communication by the investigator to the sponsor. All AESIs, whether they are SAEs or not, must be reported immediately (within 24 hours) to the sponsor. The sponsor has determined that the events listed below (whether considered serious or non-serious by investigators) should be considered AESIs, and should therefore be reported within 24 hours:

- 1) In relation to bosutinib:
 - A. Grade 3-4 diarrhea
 - B. Grade 3-4 nausea and vomiting
 - C. Potential drug-induced liver injury showed by abnormal values in liver enzyme (ALT increased and AST increased) concurrent with abnormal elevation in total bilirubin that meet the criteria outlined below:
 - a. Patients with AST or ALT and total bilirubin baseline values within the normal range who subsequently present with AST or ALT ≥ 3 times the upper limit of normal concurrent with a total bilirubin $\geq 2 \times$ ULN with no evidence of hemolysis and an alkaline phosphatase $\leq 2 \times$ ULN or not available;
 - b. For patients with preexisting ALT or AST or total bilirubin values above the upper limit of normal, the following threshold values should be used:
 - i. For patients with pre-existing AST or ALT baseline values above the normal range: AST or ALT ≥ 2 times the baseline values and $\geq 3 \times$ ULN, or $\geq 8 \times$ ULN (whichever is smaller).
 - ii. For patients with pre-existing values of total bilirubin above the normal range: Total bilirubin increased by one time the upper limit of normal or ≥ 3 times the upper limit of normal (whichever is smaller).

D. Myelosuppression (Anemia, Neutropenia, Leukopenia) considered clinically significant by the investigator.

E. Hemorrhage considered clinically significant by the investigator

F. Infection

G. Skin disorders (Rash) considered clinically significant by the investigator

H. Clinically significant immunological events (Hypersensitivity)

I. Renal dysfunction (increased blood creatinine considered clinically significant by the investigator)

J. Pleural effusions

K. Clinically significant cardiac events (QT prolongation, atrial fibrillation, sinus bradycardia, tachycardia, supraventricular tachycardia, bradycardia, premature ventricular contractions, pericardial effusion, right bundle branch block, sinus tachycardia, or premature atrial contractions).

2) In relation to atezolizumab:

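### The laboratory incidence table counts only abnormalities called clinically significant, a term neither document defines, although CTCAE-covered results are graded by rule; the two AESI lists also need reconciling

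*Protocol*

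**What the plan says.** For laboratory tests that CTCAE v5.0 covers, Protocol 15.3.3 states that "the study's biostatistician and reporting team will grade laboratory data accordingly", with Grade 0 for every non-missing value that does not reach Grade 1. Tests outside CTCAE are handled differently: "For laboratory tests where grades are not defined by CTCAE, results will be graded by the low/normal/high classifications based on laboratory normal ranges".

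The first planned summary is the "number and percentage of patients with clinically significant laboratory abnormalities, by parameter and worst post-baseline CTCAE grade". Its next sentence counts each patient once, at the worst post-baseline grade, whatever the baseline status. SAP 6.9 repeats this bullet. Neither document defines clinical significance there or names a judge.

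The other planned laboratory outputs carry no such restriction. They are "shift tables using CTCAE grades to compare baseline to the worst on-treatment value", low/normal/high shift tables for uncovered tests, and a "listing of all laboratory data with values flagged to show the corresponding CTCAE grades".

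Elsewhere, Protocol 13.2 gives four routes by which an abnormal result becomes an AE. One is that the "Test result is considered to be clinically significant by the investigator or sponsor". Protocol 13.9.1 uses similar qualifiers in its AESI list, for example "Myelosuppression (Anemia, Neutropenia, Leukopenia) considered clinically significant by the investigator". SAP 6.9 gives a different AESI list of eight entries.

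**The concern.** Grading by the biostatistics team is reproducible: the same values give the same grade at every centre. The incidence table then adds a judgement that is not reproducible as written, because nobody is named to make it and no criterion is set. The trial is open label, runs at up to 10 centres, and has safety as its primary objective.

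Three things follow for this table. Its percentages can lie below the graded incidence. They can differ between centres for reasons unrelated to toxicity. They can disagree with the shift tables for the same patients.

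The bullet also leaves open which grade is shown when a patient's worst value was not the one judged significant, so two programmers could produce different tables from the same data.

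**Working it through.** **Denominator.** Protocol 15.5 assumes that at most 15% of 36 patients will not go on to the combination: 36 × (1 − 0.15) = 30.6, which reproduces the stated 30-31. One patient is 1/31 = 3.2 points in the combination phase, or 1/36 = 2.8 points over all treated patients.

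**Direction.** Let k be the number of patients with a graded abnormality on a parameter, f the share of them called clinically significant, and N the denominator. The filtered rate is k × f / N with f ≤ 1, so it cannot exceed k / N. This holds for any-grade and for grade-or-worse counts. It need not hold for a single-grade row, because a patient moved from Grade 3 to Grade 2 raises the Grade 2 row.

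**Size.** The documents give neither k nor f. The figures below assume k = 12, with exact (Clopper-Pearson) 95% intervals.

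| Share called significant (f) | N = 31 | N = 36 |
|---|---|---|
| 1 (no filter) | 12/31 = 38.7% (21.8-57.8) | 12/36 = 33.3% (18.6-51.0) |
| 0.75 | 9/31 = 29.0% (14.2-48.0) | 9/36 = 25.0% (12.1-42.2) |
| 0.50 | 6/31 = 19.4% (7.5-37.5) | 6/36 = 16.7% (6.4-32.8) |
| 0.25 | 3/31 = 9.7% (2.0-25.8) | 3/36 = 8.3% (1.8-22.5) |

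At f = 1 the filter changes nothing.

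**Ambiguity.** Take a patient with a Grade 3 value judged not significant and a later Grade 2 value judged significant.
- If the filter selects patients and the grade is then the worst observed, the patient appears at Grade 3.
- If the filter selects values, the patient appears at Grade 2.
- If the worst value must itself be significant, the patient is not counted.

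The CTCAE shift table shows Grade 3 under every reading. If neither value is judged significant, the patient drops out of the incidence table and stays in the shift table.

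**AESI lists.** Protocol 13.9.1 has 11 bosutinib items (A-K) and 10 atezolizumab items (A-J).
- Six of the 11 bosutinib items carry the significance qualifier: D, E, G, H, I and K. That is 6 of 21 over both lists.
- Four of the six (D, E, G, I) name the investigator as judge.
- Two of the six (D, myelosuppression, and I, creatinine) rest on blood results. The other four are hemorrhage, rash, hypersensitivity and cardiac events.
- The SAP 6.9 list has seven vascular or coronary entries and a catch-all for anything the investigator thinks important. None of the six protocol items is named among its AESIs.

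**The case against.** The strongest reply is that the graded information is already planned. The shift tables and the full listing are unfiltered, and shift-table totals give worst-grade counts by parameter. That is largely right and limits the damage. It is not complete: the shift tables use the worst on-treatment value and the incidence table the worst post-baseline value, while blood counts and chemistry are also drawn 28 days after the last dose (Protocol 12.15.1 and 12.15.2). A listing is also not a percentage.

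A second reply is that many Grade 3-4 values leave little to opinion. Under Protocol 13.2 a result that changes study drug dosing is reportable as an AE on that ground alone. The dose-modification rules call for withholding or interruption for Grade 3-4 hematologic toxicity (Table 2), transaminases above 5 × ULN (Table 1), and Grade 3-4 amylase or lipase elevation (Table 9). This stands as a reason to expect f to be closer to 1 for severe values. However, 15.3.3 does not refer to 13.2, so it is unstated whether meeting any of those four routes makes a result clinically significant for the table.

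A third reply is that counting regardless of baseline pushes the rate up. That rule applies with or without the filter, so it does not offset it.

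Stronger readings are tempting but not supported:
- *That the primary safety percentages as a whole depend on opinion and understate toxicity.* Protocol 15.3.2 and SAP 6.5 summarise AEs by organ class or term, grade and causality without this filter. A rash or hemorrhage below the AESI qualifier still counts as a treatment-emergent AE. Only AEs that originate as laboratory findings are touched, through 13.2. An actual shortfall is possible but not shown.
- *That every laboratory value has a CTCAE grade.* Uncovered tests are classed low/normal/high.
- *That the bullet contradicts itself.* One reading, the first above, satisfies both of its sentences. It is ambiguous, not impossible.
- *That the qualifiers in 13.9.1 fix the AESI percentages.* That section is framed as a 24-hour reporting trigger, and the SAP lists different events.
- *That thrombocytopenia escapes the safety analysis because item D omits it,* although Protocol 11.6.1.2 says "Dose reductions are recommended for severe or persistent neutropenia and thrombocytopenia". Platelets are part of the blood count and the laboratory tables, and Grade 4 thrombocytopenia is among the DLT criteria.

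**Conclusion.** The point holds for one table. The laboratory incidence summary in Protocol 15.3.3 and SAP 6.9 rests on an undefined judgement although rule-based grades will exist for CTCAE-covered tests. Its any-grade and grade-or-worse percentages can only equal or fall below the graded incidence. The amount cannot be derived from the documents: the table of assumed shares runs from no difference to 38.7% against 9.7%, and none of those shares is a prediction. Variation between centres and disagreement with the shift tables are possible consequences, not demonstrated ones.

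This is a modest reporting weakness in a descriptive, exploratory study. It does not affect sample size, error rates or power. It merits correction because the change is cheap and the table serves the primary objective.

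The AESI mismatch is a separate defect. Until the protocol and SAP lists agree, no AESI percentage is defined, and rewording the qualifiers in 13.9.1 alone would not settle it.

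**What to change.** In the first summary bullet of Protocol 15.3.3 and of the laboratory part of SAP 6.9, delete the words clinically significant. The table then counts every patient, by parameter, at the worst post-baseline CTCAE grade, with low/normal/high categories for tests CTCAE does not cover. Add a separate column for patients with an abnormality judged clinically significant, and state who makes that judgement.

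Separately, reconcile the AESI list in Protocol 13.9.1 with the list in SAP 6.9 before any AESI table is programmed. State which events are tabulated and by what criteria, and whether the cytopenias named in item D are meant to be exhaustive. The treatment-emergent AE tables need no change.

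The laboratory change costs one phrase in each document, slightly longer tables, and cumulative rates equal to or higher than those under the filter. Because patients are counted regardless of baseline, the unfiltered rows will include abnormalities already present at entry; the planned shift tables show which these are. The AESI reconciliation needs a clinical decision on the list and takes more work than an edit of one phrase.
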